6.2. Exclusion Criteria

Subjects will be excluded from study enrollment if they meet any of the following criteria at screening and/or enrollment:

- [8] are investigative site personnel directly affiliated with this study and their immediate families. Immediate family is defined as a spouse, biological or legal guardian, child, or sibling.
- [9] are Lilly or Covance employees.
- [10] are currently enrolled in a clinical study involving an investigational product or any other type of medical research judged not to be scientifically or medically compatible with this study.
- [11] have known allergies to lasmiditan, sumatriptan, related compounds, or any components of the formulations of lasmiditan and sumatriptan.
- [12] are persons who have previously received the investigational product in this study, who have been withdrawn from this study, or who have received lasmiditan in any other study investigating lasmiditan within the 3 months prior to screening.
- [13] have participated (dosed with any investigational product), within the 30 days prior to Day -1, in a clinical study involving an investigational product. If the previous investigational product has a long half-life, 5 half-lives or 30 days (whichever is longer) should have passed.
- [14] have a history of, or ECG findings of, clinically significant bradycardia, heart block, tachy or brady arrhythmias, or have any other abnormality in the 12-lead ECG that, in the opinion of the investigator, increases the risks associated with participating in the study.
- [15] have a history, signs, or symptoms of arrhythmia or Wolff Parkinson White syndrome that could affect the subject's safety.
- [16] have an estimated glomerular filtration rate (eGFR) of <60 mL/min/1.73 m² as determined by the CKD-EPI equation:
 - GFR = $141 \times \text{minimum}(\text{Scr/k}, 1)^{\alpha} \times \text{maximum}(\text{Scr/k}, 1)^{-1.209} \times 0.993^{\text{Age}} \times (1.018 \text{ if female}) \times (1.159 \text{ if black}).$
 - Scr is serum creatinine; κ is 0.7 for females and 0.9 for males; α is -0.329 for females and -0.411 for males.

- Minimum indicates the minimum of Scr/κ or 1; maximum indicates the maximum of Scr/or 1.
- [17] have a resting SBP >135 mmHg and DBP >85 mmHg at screening. Additional assessments may be performed to confirm eligibility.
- [18] have a history of syncope, presyncope, uncontrolled vertigo, postural dizziness, or being at risk for falls, as judged to be clinically significant by the investigator, or have orthostatic decreases in SBP of >20 mmHg, or have orthostatic decreases in DBP of >10 mmHg at screening. May be repeated on 1 occasion if asymptomatic.
- [19] have a supine PR of <50 or >90 bpm at screening. Additional assessments may be performed to confirm eligibility.
- [20] have significant history of or current cardiovascular, respiratory (including bronchospasm or bronchial asthma, or chronic obstructive airways disease), hepatic, renal, gastrointestinal, endocrine, hematological, or neurological disorder, or a condition capable of significantly altering the absorption, metabolism, or elimination of drugs; of constituting a risk when taking the study medication; or of interfering with the interpretation of data. Appendectomy, splenectomy, and cholecystectomy are considered as acceptable.
- [21] have a history, signs, or symptoms of vasospastic coronary artery disease.
- [22] a history of allergic reactions to medications or food products.
- [23] have known or ongoing neuropsychiatric disorders (for example, manic depressive illness, schizophrenia, depression) considered as clinically significant by the Investigator.
- [24] show a history of central nervous system (CNS) conditions such as strokes, transient ischemic attacks, significant head trauma, seizures, CNS infections, migraines, brain surgery or any other neurological conditions that, in the opinion of the Investigator, increase the risk of participating in the study.
- [25] have a clinically significant abnormality in the neurological examination.
- [26] have a history, signs, or symptoms of Raynaud's phenomenon, hypertension, ischemic bowel disease, or peripheral vascular disease.
- [27] have an average weekly alcohol intake that exceeds 21 units per week (males up to age 65), and 14 units per week (females), or are unwilling to stop alcohol consumption 48 hours prior to admission in Period 1, and whilst resident at the CRU. At all other times, subjects must agree to consume no more than 2 units per day (1 unit = 12 oz or 360 mL of beer; 5 oz or 150 mL of wine; 1.5 oz or 45 mL of distilled spirits).
- [28] currently use, or within the past 1 year used recreational drugs, or showed evidence of substance dependence within the past 6 months based on history at the screening visit.

- [29] are unwilling to refrain from tobacco- or nicotine-containing products from 3 months prior to screening until discharge from the study.
- [30] have received centrally active drugs or those affecting peripheral cholinergic transmission within the 3 months prior to Day -1.
- [31] use of monoamine oxidase-A inhibitors and other drugs associated with serotonin syndrome (i.e. selective serotonin reuptake inhibitors, selective serotonin-norepinephrine reuptake inhibitors, tricyclic antidepressants, and 5-HT1 agonists) within the 3 months prior to the first dosing occasion.
- [32] intend to use over-the-counter or prescription medication, including dietary supplements, within 14 days prior to dosing and until study discharge (apart from occasional acetaminophen, hormonal contraception, or HRT).
- [33] show evidence of human immunodeficiency virus (HIV) infection and/or positive human HIV antibodies.
- [34] show evidence of hepatitis C and/or positive hepatitis C antibody.
- [35] show evidence of hepatitis B and/or positive hepatitis B surface antigen.
- [36] are women with a positive pregnancy test or who are lactating.
- [37] have donated blood of more than 500 mL within 1 month prior to the screening visit.
- [38] in the opinion of the investigator or sponsor, are unsuitable for inclusion in the study.

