5.5. Justification for Dose

The dose level of 200 mg lasmiditan has been well tolerated in previous studies of healthy subjects. This dose level is expected to be the highest recommended single dose for lasmiditan.

The dose of sumatriptan (100 mg) is within the range used in clinical practice. More detailed information can be found in the Sumatriptan Package Insert.

6. Study Population

Eligibility of subjects for the study will be based on the results of screening medical history, physical examination, vital signs, clinical laboratory tests and ECG.

The nature of any conditions present at the time of the physical examination and any preexisting conditions will be documented.

Screening may occur up to 28 days prior to enrollment (Day 1). Subjects who are not enrolled within 28 days of screening may be subjected to an additional medical assessment and/or clinical measurements to confirm their eligibility.

Prospective approval of protocol deviations to recruitment and enrollment criteria, also known as protocol waivers or exemptions, are not permitted.

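### Exclusion [17] joins its systolic and diastolic limits with *and*, so read literally a resting pressure above only one limit does not exclude

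*Protocol*

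**What the plan says.** Protocol Section 6.2, criterion [17], excludes those who "have a resting SBP >135 mmHg and DBP >85 mmHg at screening". It adds that further assessments may be made to confirm eligibility.

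The lead-in to the list reads "Subjects will be excluded from study enrollment if they meet any of the following criteria at screening and/or enrollment". One criterion is therefore enough to exclude, but that rule works across numbered criteria and not between the two halves of [17].

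Three other criteria could catch raised blood pressure:
- [20] covers significant cardiovascular and other disorders, including conditions capable "of constituting a risk when taking the study medication; or of interfering with the interpretation of data".
- [26] covers those who "have a history, signs, or symptoms of Raynaud's phenomenon, hypertension, ischemic bowel disease, or peripheral vascular disease".
- [38] covers those who, "in the opinion of the investigator or sponsor, are unsuitable for inclusion in the study".

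None of them states a blood-pressure value. Section 6 adds: "Prospective approval of protocol deviations to recruitment and enrollment criteria, also known as protocol waivers or exemptions, are not permitted". The SAP has no eligibility text that alters [17].

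**The concern.** In ordinary logic a criterion of the form *X above a and Y above b* is met only when both parts are true. A candidate with isolated systolic or isolated diastolic elevation therefore passes [17] as worded. The plan's background suggests that this was not intended: hypertension is excluded in [26], and Section 3.1 records that sumatriptan raises blood pressure and is contraindicated in moderate, severe and mild uncontrolled hypertension.

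What is at stake is the safety of subjects and a clear definition of the population. Section 3.3 expects no therapeutic benefit for them. Each is to receive sumatriptan 100 mg twice (Treatments A and C), once together with lasmiditan 200 mg, and the cardiovascular effect of that combination is what the study sets out to measure. Section 6.1 admits ages up to 65 and BMI up to 35 kg/m², so one-sided elevation is plausible. Two investigators could decide differently on 138/80 mmHg. It would also be unclear whether enrolling that subject was a protocol deviation.

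**Working it through.** **1. The criterion as logic.** Inputs: the limits 135 and 85 mmHg from [17].

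| Reading (mmHg) | SBP >135 | DBP >85 | Met under *and* | Met under *or* |
|---|---|---|---|---|
| 130/80 | no | no | no | no |
| 138/80 | yes | no | no | yes |
| 130/88 | no | yes | no | yes |
| 160/85 | yes | no | no | yes |
| 180/84 | yes | no | no | yes |
| 135/110 | no | yes | no | yes |
| 136/86 | yes | yes | yes | yes |

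The two readings differ whenever exactly one limit is exceeded.

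**2. How the same list words similar rules.**
- [18] separates its orthostatic systolic and diastolic limits with *or*: "or have orthostatic decreases in DBP of >10 mmHg at screening".
- [33] to [35] use *and/or* where either condition suffices, for example "show evidence of human immunodeficiency virus (HIV) infection and/or positive human HIV antibodies".
- [27] puts *and* between two alcohol limits, but labels one for males and one for females, so each plainly applies separately.
- [17] concerns two measurements on one person and has no such label.

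**3. How many candidates this touches.** The documents give no distribution of screening blood pressure, so this step rests on assumptions: bivariate normal, mean SBP 115, 120 or 125 (SD 10 or 12), mean DBP 70, 75 or 78 (SD 7 or 9), correlation 0.5, 0.6 or 0.7. That is 3 × 3 × 2 × 2 × 3 = 108 combinations.

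Let S be SBP >135, D be DBP >85, and P(both) the bivariate normal upper-tail probability.
- P(either) = P(S) + P(D) − P(both)
- P(only one) = P(S) + P(D) − 2 P(both)
- Share of exceedances that [17] misses = 1 − P(both)/P(either)

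Middle case, mean 120/75, SD 12/9, correlation 0.6:
- z for SBP = (135 − 120)/12 = 1.25, so P(S) = 0.1056
- z for DBP = (85 − 75)/9 = 1.11, so P(D) = 0.1333
- P(both) = 0.0489
- P(either) = 0.1056 + 0.1333 − 0.0489 = 0.190
- P(only one) = 0.1056 + 0.1333 − 0.0978 = 0.141
- Share missed = 1 − 0.0489/0.190 = 0.743

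| Extreme over the 108 combinations | Scenario | P(either) | P(both) | Result |
|---|---|---|---|---|
| Lowest share missed | 125/78, SD 12/9, r 0.7 | 0.300 | 0.120 | 0.600 |
| Highest share missed | 125/70, SD 12/7, r 0.5 | 0.207 | 0.011 | 0.947 |
| Lowest P(only one) | 115/70, SD 10/7, r 0.7 | 0.033 | 0.006 | 0.027 |
| Highest P(only one) | 125/78, SD 12/9, r 0.5 | 0.327 | 0.094 | 0.234 |

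These figures describe [17] on its own, before [20], [26] and [38] remove anyone.

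**4. Effect on the sample size.** Section 10.1 states a 90% CI half-width of at most 4.6 mmHg with 90% probability, for 30 completers and SD 12.7 mmHg. The check is t(0.95, 29) × 12.7/√30 × √(χ²(0.90, 29)/29) = 1.699 × 12.7/5.477 × √(39.09/29) = 4.57, which reproduces the stated figure. Its only data inputs are the number of completers and the SD of the within-subject change, so correcting [17] changes nothing there.

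**The case against.** The strongest reply is that this is a slip that no competent Phase 1 unit would apply literally.

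- **Drafting style.** Elsewhere the list uses *and* where either item plainly suffices: [8] (site personnel and their families) and [31] (several drug classes). This is fair as a comment on style. But those criteria join categories of people or drugs; [17] sets two numeric conditions on one reading, where the literal sense of *and* is the natural one.
- **Other criteria.** A markedly raised reading such as 160/85 mmHg is naturally a sign of hypertension under [26], and [20] and [38] give further grounds. The bar on waivers does not stop a site from excluding under any of these. This stands and limits the consequence: [17] alone does not admit subjects in whom sumatriptan is contraindicated. It does not supply a number for either pressure alone, and neither does the provision for additional assessments.
- **Borderline readings.** Under the same assumptions at correlation 0.6, 50% to 82% of candidates above only one limit are within 5 mmHg of it (68% in the middle case). Dosing is inpatient, with supine vital signs before dosing and at 1, 2, 4 and 24 hours and ambulatory readings every 20 minutes while awake. This also stands. Yet borderline readings are where a stated limit is most needed to make decisions consistent.
- **Assumed magnitude.** The range for all candidates is almost ninefold and is not net of the other criteria. The number actually enrolled because of the wording is unknown and could be near zero. That is accepted.

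**Conclusion.** The concern holds. As written, the only numeric upper limit on resting blood pressure applies only when both pressures are high, and one-sided elevation is left to judgement. The evident intent, from [26] and Section 3.1, is that either limit should exclude.

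The logical result needs no assumption. The size does: across the assumed distributions, 60% to 95% of candidates above at least one limit fall outside [17] (74% in the middle case), which is about 3% to 23% of all candidates. How many would then be enrolled cannot be derived from the documents.

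This is an eligibility and safety wording fault that should be corrected. It does not contradict [26] and does not affect the model or the treatment contrasts.

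**What to change.** In Protocol Section 6.2, criterion [17], replace *and* with *and/or*, so that a resting SBP >135 mmHg and/or a DBP >85 mmHg at screening excludes. This is the form already used in [33] to [35]. Keep both limits and the sentence on additional assessments, so that a borderline reading can still be checked before the subject is rejected.

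The cost is a one-word protocol edit and possibly a few more screen failures. No change to the SAP is needed. If sites already apply either limit, the edit only brings the text into line with practice.

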6.2.1. Rationale for Exclusion of Certain Study Candidates

Criteria [1] through [7] define a healthy population suitable for evaluation in a Phase 1 study. Criteria [8] and [9] prevent conflict of interest in study participants. Criteria [10] through [38] predominantly exclude medical conditions, medication intolerance, and concomitant medication use that may confound the assessment of study endpoints.

6.3. Lifestyle and/or Dietary Requirements

Throughout the study, subjects may undergo medical assessments and review of compliance with requirements before continuing in the study.

6.3.1. Meals and Dietary Restrictions

Lasmiditan and sumatriptan will be administered after an overnight fast of at least 8 hours. On Day 1 of each treatment period, subjects will abstain from water 1 hour before and after dosing (except for water given with the dose). Subjects will remain fasting for approximately 3 hours postdose, at which time a meal will be served.

6.3.2. Caffeine, Alcohol, and Tobacco

Caffeine – Subjects will refrain from consuming xanthine- or caffeine-containing food and drinks from 48 hours prior to admission in Period 1, and whilst resident at the CRU.

Alcohol – Subjects will not consume alcohol for 48 hours prior to admission in Period 1, and whilst resident at the CRU. At all other times, subjects must consume no more than 2 units per day (1 unit = 12 oz or 360 mL of beer; 5 oz or 150 mL of wine; 1.5 oz or 45 mL of distilled spirits).

Tobacco – Subjects will refrain from smoking from 3 months prior to screening until discharge from the study.

Grapefruit – Subjects will refrain from consuming grapefruit and grapefruit-containing products from 7 days prior to Day 1 in Period 1, and until study discharge.

6.3.3. Activity

No strenuous exercise will be allowed for 48 hours prior to admission in each treatment period until after the follow-up visit.

6.4. Screen Failures

Individuals who do not meet the criteria for participation in this study (screen failure) may not be re-screened.

7. Treatment

7.1. Treatment Administered

Investigational products used in this study are shown in Table LAHU.3.

Tablets of lasmiditan and sumatriptan will be administered orally with approximately 240 mL of room temperature water, in a sitting position. Tablets of lasmiditan and sumatriptan will be administered in the morning of Day 1 of each treatment period. Subjects will not be allowed to lie supine for 2 hours after dosing, unless clinically indicated or for study procedures.

Table LAHU.3. Treatments Administered

		~ .	
Treatment Name	Lasmiditan	Sumatriptan	Placebo (lasmiditan)
Dosage Formulation	film-coated tablet	film-coated tablet	film-coated tablet
Unit Dose	$(1 \times 200$ -mg) tablets/	$(1 \times 100\text{-mg})$ tablets/	
Strength/Dosage Level	200 mg lasmiditan	100 mg sumatriptan	
Route of Administration	Oral	Oral	Oral
Dosing Instructions	1 tablet taken in the morning	1 tablet taken in the mornin	ng 1 tablet taken in the morning
	of Day 1	of Day 1	of Day 1

The investigator or designee is responsible for:

- explaining the correct use of the investigational product(s) to the site personnel
- verifying that instructions are followed properly
- maintaining accurate records of investigational product dispensing and collection
- and returning all unused medication to Lilly or its designee at the end of the study

Note: In some cases, sites may destroy the material if, during the investigative site selection, the evaluator has verified and documented that the site has appropriate facilities and written procedures to dispose of clinical materials.

7.1.1. Packaging and Labeling

Each tablet of lasmiditan contains 200 mg of active ingredient and is provided as bulk supplies in bottles. Sumatriptan will be sourced by the investigative site.

Both lasmiditan and sumatriptan tablets are round and 10 mm in diameter. Placebo tablets look similar to both lasmiditan and sumatriptan tablets, but contain no active ingredient. Placebo tablets will be provided in similar bulk bottles as lasmiditan.

The investigational product will be labeled according to the country's regulatory requirements.

7.2. Method of Treatment Assignment

All subjects will participate in 4 treatment periods. The treatments are as follows:

- Treatment A: lasmiditan 200 mg + sumatriptan 100 mg
- Treatment B: lasmiditan 200 mg + placebo
- Treatment C: sumatriptan 100 mg + placebo
- Treatment D: placebo + placebo

Each subject will be randomized to one of 4 treatment sequences in a William's square design (i.e., ABCD, BCDA, CDAB, and DABC) using a computer-generated allocation schedule.

